14.1 Characteristics of an Adverse Event

14.1.1 Severity of the Adverse Event

Severity of AEs will be determined using the following scale:

- Mild: The patient is aware of a sign or symptom, but it is easily tolerated
- Moderate: Discomfort or interference with usual activity
- Severe: Incapacitating, with inability to engage in usual activity

14.1.2 Relationship of an AE and SAE to the Study Device

The relationship of the adverse event to the study device is defined as follows:

Definite: An adverse event has a definite determination that it was caused due to the device.

Probable: An adverse event has a strong temporal relationship to study device or recurs on rechallenge, and another etiology is unlikely or significantly less likely.

Possible: An adverse event has a strong temporal relationship to study device, and an alternative etiology is equally or less likely compared to the potential relationship to study device.

Unrelated - The AE is clearly NOT related to the device.

14.2 Definitions of Adverse Event and Adverse Device Effect

An adverse event (AE) is any untoward medical occurrence, unintended disease or injury or any untoward clinical signs (including an abnormal laboratory finding) in study participants, whether

or not related to the investigational device. This should relate to baseline information whenever available.

An adverse device effect (ADE) is an adverse event related to the use of the investigational device. In this study the ADE is refers to "side effect" or "complications".

14.3 Definition of Serious Adverse Event

A serious adverse event (SAE) is an adverse event, that

- a) led to death,
- b) led to serious deterioration in the health of the subject, that either resulted in
 - 1) a life-threatening illness or injury, or
 - 2) a permanent impairment of a body structure or a body function, or
 - 3) in-patient or prolonged hospitalization, or
 - 4) medical or surgical intervention to prevent life-threatening illness or injury or permanent impairment to a body structure or a body function,

- c) led to fetal distress, fetal death or a congenital abnormality or birth defect

It is responsibility of site PI to report any Serious Adverse Event or Serious Adverse Device Event to Theranica Bioelectronics, within 24 hours to:

Theranica Bioelectronics

[name]

[contact]

Fax: [name]

Email: [contact]

A Serious device related adverse effect (SADE) is an adverse event related to the use of the investigational device and that is considered by regulations and definitions as Serious.

14.4 Device Deficiency

Device deficiency is an inadequacy with respect to the device's identity, quality, durability, reliability, safety, or performance, such as a malfunction, failure, use error or inadequate labeling. Device deficiencies may or may not be associated with an adverse event.

All device deficiencies will be entered in the eCRF. Device deficiencies that were associated with an SAE or that could have led to an SAE if a) suitable action had not been taken or b) intervention had not been made or c) if circumstance had been less fortunate, will be reported within 24 hours of occurrence. If possible, the device(s) associated with a malfunction or failure should be retained until arrangements for its collection are made by Theranica.

Device deficiencies will be summarized and reported in the clinical study report and will be reported to the regulatory authorities per country's applicable reporting requirements.

14.5 Time-frame for Investigator Reporting AE to Sponsor, EC, RA

Serious adverse events, whether or not related to the device, and whether anticipated or unanticipated, must be reported to the sponsor within 24 hours of learning of the event occurrence by the site staff. This requirement is in addition to, and does not replace, other investigator responsibilities for adverse event reporting. Notification on a SAE is forwarded to

Theranica designated contact person. Additionally, SAEs should be reported by the site to the involved IRB/EC and Regulatory Authorities as applicable.

Unanticipated device related adverse events shall be reported to the sponsor within 48 hours of learning of the event occurrence by the site staff.

In addition, device related side effects shall be reported to the sponsor and documented in monitoring visit/phone call summary.

Any AE that results in withdrawal from observation in the study must be reported to the sponsor within 24 hours after the decision to withdraw the patient is made.

Any death occurring during the study must be reported to the sponsor within 24 hours of discovery of the event. "Death" should not be reported as an AE, the cause of death should be reported as an AE. The only exception is "Sudden Death" when the cause is unknown. A copy of the death records, death certificate and an autopsy report (if performed) must be provided to the sponsor as soon as possible.

The sponsor is responsible for relaying adequate information on SAEs to the regulatory authorities per country's applicable reporting requirements.

14.6 Adverse Event Reporting Forms

The eCRFs for AE or SAE will include all relevant information of the AE or SAE with regards to onset and resolution time, grade, causality to device, treatment given etc.

14.7 Foreseeable Complications and Anticipated Adverse Device Related Effects.

Possible adverse events associated with Transcutaneous Electrical Nerve Stimulation include, but are not limited to the following:

- Likely
 - Minor skin irritation from wearing the device, which disappears shortly after the treatment is over.
- Less Likely
 - Red marks at the site of stimulation, that disappear shortly after the treatment is over.
 - Possible sensation of slight warmth where the device touches the skin. This disappears shortly after the treatment is over.
 - A sensation of itching or tingling or stinging at the site of stimulation, which disappears shortly after the treatment is over.
 - Slight muscle fatigue or weakness in arm where the device is applied, which disappears shortly after the treatment is over.
- Very unlikely
 - Slight muscle spasms in the arm where the device is applied, which disappears shortly after the treatment is over.

The following migraine symptoms are foreseeable and will not be considered as device related: headache, nausea, light sensitivity, sensitivity to noise or odors, stomach upset, abdominal pain, loss of appetite, cold or heat sensation, paleness, fatigue, dizziness, fever (rare), blurred vision, bright flashing dots or lights, blind spots, wavy or jagged lines (aura).

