Patient global impression of change will be summarized by descriptive statistics per treatment group and compared between the groups with a t-test.

Ease of use will be summarized by descriptive statistics.

7.8.6 *Safety Analysis:*

The primary safety variable, the cumulative incidence (and 95% CI) of device related adverse events (AEs) throughout the study, will be presented in tabular format and will include incidence tables by severity.

Adverse event rates will be compared between the study groups with a chi-squared test.

Serious adverse events will be listed and discussed individually.

Treatment tolerability will be compared between the study groups, the number and percent of subjects who fail to complete the study and the number and percent of subjects who fail to complete the study because of Adverse Events will be presented as well.

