8. Sensation of heat at the location of the device?
 9. None
 10. Mild
 11. Moderate
 12. Severe
9. Overall, how would you rate the study and your experience with the device?
 1. Excellent
 2. Very good
 3. Good
 4. Fair
 5. Poor
10. How user friendly and intuitive was the App?
 1. Extremely friendly/intuitive

2. Very friendly/intuitive
3. Somewhat friendly/intuitive
4. Not so friendly/intuitive
5. Not friendly/intuitive at all

11. To what extent did you like using the device?

- a. Liked it a lot
- b. Liked it
- c. Did not like it so much
- d. Disliked it very much

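### Section 14.7 rules listed migraine symptoms not device-related in advance, against the case-by-case scale in 14.1.2, so the primary safety incidence can be under-counted

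*Combined protocol and SAP*

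**What the plan says.** Section 14.7 contains two lists. The first gives the anticipated device effects, all local and transient. Among them are "Possible sensation of slight warmth where the device touches the skin" and "Slight muscle fatigue or weakness in arm where the device is applied, which disappears shortly after the treatment is over". The second opens with "The following migraine symptoms are foreseeable and will not be considered as device related" and runs from headache and nausea to visual aura, including "cold or heat sensation, paleness, fatigue, dizziness, fever (rare), blurred vision". It makes no exception for onset during stimulation, worsening, location or recurrence.

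Section 14.1.2 sets the general method: "The relationship of the adverse event to the study device is defined as follows", followed by four levels (Definite, Probable, Possible, Unrelated). The levels rest on timing, on recurrence at re-exposure and on how likely another cause is. The lowest positive level begins "Possible: An adverse event has a strong temporal relationship to study device, and an alternative etiology is equally or less likely". Section 14.6 has the eCRF record causality for each AE.

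Section 14.8 sends SAEs, USADEs and ADEs, as the investigator has classed them, to adjudication, and the adjudicated events are the basis for reporting. Section 7.8.6 names the safety result that depends on all this: "The primary safety variable, the cumulative incidence (and 95% CI) of device related adverse events (AEs) throughout the study". Section 6.3.4 also makes AEs of any cause a safety endpoint, and Section 7.8.6 compares AE rates between arms.

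**The concern.** The primary safety variable is a count of events judged related to the device. For the listed symptoms, Section 14.7 settles that judgement before any event occurs. An investigator faced with dizziness that starts with stimulation and returns at the next treated attack has two instructions that cannot both be followed: grade it under 14.1.2, where it could reach Probable, or call it unrelated under 14.7.

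If 14.7 is followed, a non-serious event leaves the device-related count and nothing later in the plan re-examines it. Two other provisions also turn on relatedness: 48-hour reporting of unanticipated device-related events (Section 14.5) and continued follow-up of device-related events still active at the last visit (Section 14). A listed symptom would not trigger either on that ground. At stake is whether the reported incidence measures what the device does, or partly reflects a rule written beforehand.

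**Working it through.** The plan gives no expected rate of device-related AEs and no safety threshold, so there is no figure to reproduce. The check is to follow an event through the text.

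**Step 1. Path of a non-serious listed symptom, for example dizziness during stimulation.**

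| Stage | Section | Result |
|---|---|---|
| Recorded as an AE | 14.2, 14.6 | Yes |
| Graded on timing, re-exposure and other causes | 14.1.2 | Called for |
| Relatedness fixed in advance | 14.7 | Not device-related |
| Adjudicated | 14.8 | No: neither an SAE nor classed as an ADE |
| In the primary safety variable | 7.8.6 | No |
| In the all-AE endpoint and comparison by arm | 6.3.4, 7.8.6 | Yes |

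A serious listed symptom differs at one stage. Section 14.8 adjudicates every SAE for relatedness, so it can still be counted. This assumes that the adjudicators are not themselves bound by the 14.7 sentence, on which the text is silent.

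**Step 2. Direction.** Within an arm, let *a* be the proportion of subjects with at least one device-related event that 14.7 allows to be counted. Let *b* be the proportion with no such event but with at least one non-serious listed symptom that the device in fact caused.

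- Counted incidence under 14.7 = *a*
- Incidence without the exclusion = *a* + *b*
- Shortfall = (*a* + *b*) − *a* = *b* ≥ 0

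The exclusion can only remove subjects from the count. It has no effect if *b* = 0. This concerns the incidence within each arm; it says nothing about the direction of any difference between arms.

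**Step 3. Size.** The documents do not give *b*. The pilot summary in Section 4.2 reports no device-related AEs, but does not say how relatedness was judged there, so it does not supply *b* either.

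**Step 4. The overlapping terms.**

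| Device-effect list | Excluded list | Report without a location |
|---|---|---|
| Slight warmth at the contact site | Cold or heat sensation, no site given | Codable either way |
| Muscle fatigue or weakness in the treated arm | Fatigue, no site given | Codable either way |

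Section 14 makes the 14.7 list the CRF nomenclature for device-related side effects, but neither section says how to code a bare report of heat or fatigue. The end-of-study questionnaire (Appendix B) does ask by site: "Sensation of heat at the location of the device". It has no matching item for fatigue.

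**The case against.** The strongest defence is that the sentence guards against the opposite error. The device is used at migraine onset, when headache, nausea and light sensitivity are expected anyway, and a rating driven by timing could book the treated disease as a device effect. That risk is real. However, 14.1.2 does not rest on timing alone: even Possible requires that another cause be no more likely than the device, and an ordinary migraine headache would usually fail that test. Blinded rating and the sham arm deal with what remains.

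Second, the events are not lost. They remain AEs and are compared by arm. Nausea, photophobia and phonophobia are also recorded at treatment start and at 2 hours (Section 6.4.2), and freedom from each is a secondary endpoint. This stands, and it limits the harm. It does not repair the primary safety variable, and the app screens do not ask about dizziness, fatigue or blurred vision. Section 14 captures AEs during treatment through the end-of-study questionnaire and interview, and the questionnaire's prompts on bodily effects cover only itching, redness and heat at the device site.

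Third, no pass or fail decision turns on this count. The formal hypothesis (Section 7.3) and the success criterion (Section 7.8.5) concern performance only. Section 5.2 does mention unexpected device-related effects, but the plan sets no safety threshold. This also stands.

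A reader might infer that 14.7 excludes the very warmth it lists as a device effect, so that heat under the electrode could never be counted. The text does not support that. Warmth at the contact site and fatigue in the treated arm are named device effects and stay countable; only reports without a location are ambiguous.

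**Conclusion.** The plan is wrong as written on a narrow point. The categorical exclusion in 14.7 contradicts the event-by-event grading in 14.1.2 and the causality entry in 14.6. Non-serious listed events have no route back through 14.8. For these terms the primary safety incidence can be under-counted and never over-counted. The size is unknown and could be nil.

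It would be tempting to say that the incidence is under-counted, or biased toward zero whatever the data show. That goes too far: a shortfall needs at least one listed symptom that the device really caused, in a subject with no other countable event, and the documents give no rate for this. Nor are the listed events removed from the safety record; they leave only the device-related count. The performance analysis is untouched.

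**What to change.** Reconcile 14.7 with 14.1.2 and 14.8:

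- Replace the categorical exclusion with a statement that every AE, including these symptoms, is rated by the blinded investigator on the 14.1.2 scale. Events rated related then reach adjudication through the existing wording of 14.8.
- Keep the list as context that these symptoms are common in migraine.
- Tabulate the listed symptoms by arm alongside the primary safety variable.
- Separate the heat and fatigue terms by location, device site or treated arm versus general, and record the location on the AE form.

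The cost is a few words in 14.7, a location entry on the form and one table. The device-related incidence may come out slightly less favourable and may include some background migraine symptoms; the sham arm makes that interpretable. Sample size and performance analyses do not change.

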14.8 Safety Monitoring and Adjudication of Adverse Events

The sponsor will review submitted AE information and may request supplemental information if needed. For SAE, USADE and ADE (as classified by the investigator) a narrative will be prepared and adjudicated for assessing the relatedness, seriousness and possible action items required. The sponsor may ask for further information or clarification from the investigator. A summary of the adjudication results will be issued; if different than investigator's report, PI will be notified.

Adjudicated events will serve as a basis for reporting AE/SAE. Differences between site-reported events and adjudicated events will also be presented and discussed in the report.

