6.2.2 Procedures to ensure blinding

This is a double-blind study: neither the patient, nor the investigators will be aware of arm allocation of each study participant. Maintaining double blind design is a known challenge in non-invasive neuromodulation devices trials. A number of means are planned to ensure the double blind aspect of this trial.

Selection of identically looking, active sham devices as control means is only a single step aimed at maintaining blindness. Each device will be numbered with 3 digit numbers, first digit site number and two digit subject numbers. Each new patient will be provided with d next consecutive numbered device.

Adherence to randomization procedure by clinical staff is critically important.

Importance of adherence to study design and procedures will be explained to participants in the course of enrollment.

No information regarding expected stimulation perception will be provided, except for the fact that stimulation intensity adjustment control will allow to adjust intensity to "a well perceived but non-painful" level.

In order to achieve blinding, participants will be trained individually. A training clip will be used for training, in order to minimize staff exposure to participants' reaction to and tolerability of treatment intensity.

In the course of the trial, participants will not be asked directly any questions regarding treatment perception.

The clinical staff will be instructed to not engage in any discussions regarding anticipated treatment perception.

End of study questionnaire will include individual blinding assessment to examine whether the blinding was well maintained throughout the study.

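### For non-serious events, adjudication can remove but not add device-related events, and section 7.8.6 does not say whose relatedness call defines the primary safety variable

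*Combined protocol and SAP*

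**What the plan says.** Section 14.8 sets the entry rule for adjudication: "For SAE, USADE and ADE (as classified by the investigator) a narrative will be prepared and adjudicated for assessing the relatedness". Seriousness is adjudicated as well. The same section states that "Adjudicated events will serve as a basis for reporting AE/SAE" and that "Differences between site-reported events and adjudicated events will also be presented and discussed in the report". It opens with a general statement that the sponsor reviews the adverse event information it receives and may ask for more.

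Section 14.2 supplies the key definition: "An adverse device effect (ADE) is an adverse event related to the use of the investigational device". Section 14.5 treats serious events differently: "Serious adverse events, whether or not related to the device, and whether anticipated or unanticipated, must be reported to the sponsor within 24 hours".

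The synopsis names device-related adverse effects as the primary safety endpoint. Section 7.8.6 analyses it as a cumulative incidence with a 95% confidence interval, without saying whether relatedness is the investigator's or the adjudicated call. It adds that "Adverse event rates will be compared between the study groups with a chi-squared test". On blinding, section 6.2.2 says that "neither the patient, nor the investigators will be aware of arm allocation of each study participant"; it does not mention an adjudicator.

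**The concern.** Adjudication of relatedness can correct two kinds of error: events wrongly attributed to the device, and device effects that the site missed. For non-serious events the entry rule in 14.8 allows only the first correction. If the adjudicated result is also the reported one, the device-related count in that stream can fall or stay the same, but it cannot rise.

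This matters because of what the primary safety variable will mostly contain. All six device effects foreseen in section 14.7 are minor or pass shortly after treatment. The list is not exhaustive, but nothing in it would ordinarily be serious, and the pilot recorded no device-related events. The stream with the one-way rule is therefore likely to supply nearly all of the count.

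The reader of the study report would also not know which classification was primary, since 7.8.6 is silent, or whether the person making the final call knew the arm.

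**Working it through.** The documents give no expected adverse event rate, adjudication rate or reclassification rate, so there is no stated figure to reproduce. The check is one of logic, followed by an illustration.

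**Step 1: who enters.** From 14.8, an event is adjudicated if it is an SAE, a USADE or an ADE. From 14.2, an ADE is device-related. USADE is not expanded in the acronym list, but it is evidently a class of device effect, so it gives unrelated events no route. An SAE enters whatever its relatedness.

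**Step 2: possible change in the device-related count per event.**

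| Event | Investigator's call | Adjudicated? | Possible change |
|---|---|---|---|
| Non-serious | Unrelated | No | 0 |
| Non-serious | Related | Yes | −1 or 0 |
| Serious | Unrelated | Yes | 0 or +1 |
| Serious | Related | Yes | −1 or 0 |

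The non-serious rows contain no +1. The only +1 in the table comes from serious events first called unrelated.

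**Step 3: illustration.** Every rate here is an assumption, with one event per subject. Let p be the investigator-rated device-related incidence, d the share downgraded, s the incidence of SAEs called unrelated, and u the share of those upgraded. Then

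reported incidence = p × (1 − d) + s × u.

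- Non-serious stream alone, p = 5%: d = 0 gives 5.0%; d = 20% gives 5% × 0.8 = 4.0%; d = 40% gives 5% × 0.6 = 3.0%.
- Contribution of SAEs: s = 1%, u = 10% adds 0.1 point; s = 2%, u = 50% adds 1.0 point.
- Combined, p = 5%, d = 20%, larger SAE assumption: 4.0% + 1.0% = 5.0%, a net change of zero.
- Combined, p = 3%, d = 20%, larger SAE assumption: 2.4% + 1.0% = 3.4%, a rise of 0.4 point.

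The process as a whole can thus move the rate either way. If SAEs are rare, the movement is close to one-directional.

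**Step 4: missed events.** If the true non-serious incidence were 10% and sites called 80% of those events related, the investigator-rated figure would be 10% × 0.8 = 8.0%. The other 2.0 points lie outside adjudication whatever the adjudicator does.

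**Step 5: what the disclosure shows.** A table of differences between site and adjudicated calls reveals every downgrade. A non-serious event that was not adjudicated has no second call to differ from, so it cannot appear there.

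**The case against.** Much of the case on the other side stands.

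- A reader might infer that adjudication can only lower the primary safety rate. The documents do not support that: serious events are adjudicated whatever the site's call, and an upgrade raises the rate.
- A reader might infer that unrelated non-serious events get no second look at all. Section 14.8 has the sponsor review submitted event information, and section 14.6 puts causality on the event form. What is missing is a rule that takes such an event on to adjudication.
- A reader might infer that the between-arm test is biased. The chi-squared test in 7.8.6 names adverse event rates, not device-related rates. Moving an event from related to unrelated leaves the overall count in its arm unchanged. A device-related comparison could be distorted only if misclassification differed by arm.
- A reader might infer that the adjudicator is unblinded. The text is merely silent. The only role described as unblinded is the interim statistician in section 7.5.
- Missed events may be few. Section 14.1.2 reserves the unrelated grade for events clearly not caused by the device, and the end-of-study questionnaire asks every subject about itching, redness and heat at the device site. Against that, section 14.7 rules out heat sensation and fatigue as device-related while also listing slight local warmth and slight arm muscle fatigue as foreseen device effects, so a site could reasonably go either way.

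Downgrades are disclosed, and many may be right. None of this supplies a route for a non-serious event called unrelated to be reclassified, nor does it settle which call is primary.

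**Conclusion.** The point holds in limited form, as a cheap improvement. For non-serious events, adjudication under 14.8 can remove device-related events but not add them; only serious events first called unrelated can be upgraded. That the adjudicated call feeds the primary safety variable is an inference from 14.8, because 7.8.6 does not say, and this silence is itself part of the finding. The absence of any statement on adjudicator blinding calls for clarification and is not evidence of bias.

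The size cannot be derived from the documents. The figures of 5.0% to 3.0% above show only how the rule works under assumed rates. The practical weight rests on two assumptions: that serious events will be rare, and that sites will sometimes call a true minor device effect unrelated.

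**What to change.** In 14.8, have the existing adjudicator review relatedness of all adverse events on a line listing, blind to arm and to stimulation logs, and keep narratives for SAE, USADE and ADE only. This opens the missing upward route without adding narratives.

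In 7.8.6, name the relatedness classification that is primary, and present the device-related incidence by arm under both the investigator's and the adjudicated classification.

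Counting an event as related whenever either source says so need not be the primary definition. It would replace a downward ratchet with an upward one, since adjudication could then never correct a false attribution. Showing both rates gives the reader the same information.

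The cost is protocol wording and a short listing review in a trial of at most 248 evaluable patients. The reported device-related rate may come out slightly higher.
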